## 2 INTRODUCTION: BACKGROUND INFORMATION AND SCIENTIFIC RATIONALE

### 2.1 BACKGROUND INFORMATION

Over one million hospitalizations for AHF occur every year in the US. Within 30 days after hospitalization, over 25% of AHF patients will be dead or re-hospitalized. By one year after hospitalization, up to 67% of patients will be re-hospitalized and 36% will be dead. Worldwide, the costs of AHF exceed 100 billion annually. For patients aged 65 years and older, AHF is the most common and most expensive reason for hospitalization. Despite major reductions in morbidity and mortality for chronic HF, considerably less progress has been seen in AHF.

The emergency department (ED) initiates diagnosis and management for the vast majority of AHF patients. Nearly 80% of all admissions originate from the ED. Delays in diagnosis, misdiagnosis, and delayed or improper treatment are costly, associated with greater morbidity and mortality. One of the most expensive decisions in healthcare is made routinely from the ED; who gets hospitalized vs. discharged. Despite this crucial starting role, **ED AHF pharmacological management today is largely the same as 40 years ago.** In fact, guidelines state: *“the treatment of AHF remains largely opinion-based with little good evidence to guide therapy.”* Consensus statements from the American Heart Association as well as a working group from the NHLBI on ED AHF management further corroborate this lack of evidence: *“the evidence base on which this foundation of acute care is built is astonishingly thin.”* There remains a critical unmet need for evidence based ED AHF management.

Congestion is the primary reason why AHF patients present to the ED seeking medical care. Congestion is manifest by signs and symptoms of heart failure (HF) — for example, dyspnea, orthopnea, edema, and weight gain. Yet how to best assess, grade, and manage congestion is not well established. Only recently has the dosing of IV loop diuretics been studied; however patients were enrolled up to 24 hours after admission.

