1. *Logistic regression models*: We will consider three different models. First, we include all markers together with B-line measurements in the model (Model 1). Second, we will explore all main effects models that can be built using the B-line measurements along with the other markers and select the one with the best model fitting characteristic (e.g. Akaike Information Criterion or Bayesian Information Criterion) (Model 2). Third, we will explore all main effects models that can be built using only the other markers (Model 3). These models will allow us to create a discriminating score for the prediction of 30 or 90-day outcomes.

2. *Tree based nonparametric method:* We will employ the classification tree to build a nonparametric prediction model using B-lines measurements and the seven other markers. (Model 4). We will build a similar classification tree without the involvement of the B-lines measurements (Model 5).

Models 1-5 will be evaluated using data from the testing set in terms of prediction accuracy. In particular, Models 2 and 3, 4 and 5 will be compared (if there is a difference between models 2 and 3, and between 4 and 5) to understand the net reclassification rate. Statistical inference of the comparison will be performed using the bootstrap method.

---

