### 10.5 SAMPLE SIZE

Our preliminary data suggest that 25% of patients in the usual care arm will have < 15 B lines at the conclusion of ED AHF management. With 59 patients in each of the two arms, we will have 81% power to detect an effect size of 2 (i.e. 25% in the usual care versus 50% in the strategy care), where the type I error rate is controlled at 0.05 (two-sided). Considering a conservative 10% drop-out rate, we will need a total of 130 subjects.

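### Exploratory prediction Models 1-5 are to be judged on a testing set that is never defined; a hold-out from 130 patients would be imprecise, and internal validation on all patients is better

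*Combined protocol and SAP*

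**What the plan says.** Section 10.4.4 describes three logistic models and two classification trees. Model 1 contains all markers. For Model 2, "we will explore all main effects models that can be built using the B-line measurements along with the other markers", with the choice made by a criterion such as AIC or BIC. Model 3 is the same search without B-lines. Model 4 is a tree using B-lines and seven further markers, and Model 5 is a tree without B-lines. The stated product is a score: "These models will allow us to create a discriminating score for the prediction of 30 or 90-day outcomes".

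On validation there is one sentence: "Models 1-5 will be evaluated using data from the testing set in terms of prediction accuracy". Models 2 and 3, and 4 and 5, are then compared in terms of net reclassification, with bootstrap inference for the comparison. The same section also uses the bootstrap for confidence intervals and marker comparisons. It mentions neither optimism correction nor which modelling steps are repeated in a resample.

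Section 10.5 sets the size of the trial: "Considering a conservative 10% drop-out rate, we will need a total of 130 subjects". No event count or precision is given for these models. Section 10.4.3 limits covariates to one per 10 events, but only for the primary-endpoint regression.

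**The concern.** The validation sentence can be read in two main ways, and both cause trouble.

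- **Part of the trial is held out.** The subset search and the trees are fitted to a fraction of an already small number of events, and accuracy is then estimated on the few events that remain. Both the selected model and its measured accuracy depend heavily on the split.
- **Nothing is held out.** Accuracy is measured on the patients used to select the model, so it is too favourable unless the selection itself is repeated in the validation.

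At stake is the credibility of the score and of the two with-and-without-B-lines comparisons. Section 3 presents the pilot as the source of information for a larger trial, so a chance gain, or a gain hidden by chance, could carry forward.

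**Working it through.** **The plan's own figure.** Section 10.5 states: "With 59 patients in each of the two arms, we will have 81% power to detect an effect size of 2", with "25% in the usual care versus 50% in the strategy care". With pooled variance under the null, the mean proportion is 0.375.
- Null SE = √(2 × 0.375 × 0.625 / 59) = 0.0891
- Alternative SE = √((0.25 × 0.75 + 0.50 × 0.50) / 59) = 0.0861
- z = (0.25 − 1.96 × 0.0891) / 0.0861 = 0.87, so power is 80.9%

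This agrees with the stated 81%. Also 118 × 1.10 = 129.8, which gives 130. The size rests on the primary endpoint alone.

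**Event rates (assumptions).**
- 30 days: section 2.1 says that "over 25% of AHF patients will be dead or re-hospitalized", and the Protocol Summary says nearly 25%. This is background epidemiology, not a planning input. 0.25 × 130 = 32.5, about 32 events.
- 90 days: extrapolated from the 44-patient pilot in section 2.2, which reports 15 events (the components listed add to 14). 15/44 = 34%; 15/32 of those contacted = 47%. Applied to 130 patients this gives 44 to 61 events. Median pilot follow-up was 58 days.

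**Precision of one AUC.** Hanley-McNeil, with A the AUC, n1 events and n0 non-events:

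SE² = [A(1−A) + (n1−1)(Q1−A²) + (n0−1)(Q2−A²)] / (n1·n0), where Q1 = A/(2−A) and Q2 = 2A²/(1+A).

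At A = 0.70, Q1 − A² = 0.0485 and Q2 − A² = 0.0865.
- All patients (32 and 98): √[(0.21 + 1.50 + 8.39)/3136] = 0.057; × 1.96 = 0.11
- Half (16 and 49): √[(0.21 + 0.73 + 4.15)/784] = 0.081; × 1.96 = 0.16
- One third (11 and 32): √[(0.21 + 0.48 + 2.68)/352] = 0.098; × 1.96 = 0.19

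The same formula at the other rates gives:

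| Assumed event rate | All 130: events, half-width | Half test set | One-third test set |
|---|---|---|---|
| 25% (30 days) | 32, 0.11 | 16, 0.16 | 11, 0.19 |
| 34% (90 days) | 44, 0.10 | 22, 0.14 | 15, 0.17 |
| 47% (90 days) | 61, 0.09 | 30, 0.13 | 20, 0.16 |

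With 118 evaluable patients the 25% row becomes 0.115, 0.164 and 0.202.

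**Size of the search.** Counting B-lines as one term, there are 8 candidates and 2⁸ − 1 = 255 non-empty subsets. At 25%, training events per candidate are 16/8 = 2.0 after a half split and 21/8 = 2.6 after a one-third hold-out, against 32/8 = 4.0 with everyone.

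**Does resampling do better?** Simulated trials of 130 patients with 25% events and assumed coefficients, measuring RMSE of the estimated AUC against the true AUC of the model fitted to all patients:

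| Method | Full 8-term logistic (400 trials) | AIC subset search, repeated in each resample (160 trials) |
|---|---|---|
| One-third test set | 0.108 | 0.101 |
| Half test set | 0.093 | 0.098 |
| Apparent AUC, uncorrected | 0.093 (bias +0.080) | 0.078 (bias +0.063) |
| Bootstrap optimism correction | 0.059 (bias +0.011) | 0.055 (bias +0.001) |

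A further simulation with AIC selection repeated in each resample gave about 0.07 for the bootstrap against 0.10-0.11 for a split. Across these runs the error falls by about 30% (1 − 0.07/0.10) to 46% (1 − 0.055/0.101). Trees were not simulated.

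**The case against.** The plan does not say that patients will be split. A testing set could mean cross-validation folds or out-of-bag bootstrap samples, in which case every patient contributes to testing and the 16 or 11 events do not arise. This stands: the hold-out is an inference from an undefined term, and the half-widths apply only if it is what was meant. On the resampling readings the remedy is simply to write the method down.

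Three stronger readings are tempting, and the documents do not support them.
- *The plan will use these models to claim that B-lines add prognostic value.* No such claim or decision rule appears. The models are listed as exploratory, and the comparison is meant to describe reclassification.
- *The planned bootstrap ignores model selection.* The text is silent on what each resample repeats. That is unspecified, not wrong.
- *The trial has 32 events for these models.* That is a background 30-day rate applied to 130. The models may target 90 days, and the exploratory composite also counts cardiovascular ED revisits.

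Two technical limits also stand. The half-width of a single AUC is not the precision of the paired comparisons (2 v 3, 4 v 5) or of net reclassification, which is not quantified here. And 255 subsets assumes one term for B-lines, although section 10.4.4 considers both absolute number and relative change, and the seven other markers are not itemised.

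**Conclusion.** The concern holds as a minor point on an exploratory analysis. The testing set is undefined. If it is a hold-out, the 95% half-width at an AUC of 0.70 rises from 0.11 to 0.16 (half) or 0.19 (one third) at a 25% event rate, and from 0.09-0.10 to 0.13-0.14 or 0.16-0.17 at 34% to 47%. If nothing is held out, the simulations put the optimism of the apparent AUC at roughly 0.06 to 0.08. Validation on all patients does better than either in the cases simulated.

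This rests on assumed event rates, assumed coefficients in the simulations, and logistic models only. Imprecision remains afterwards: about ±0.11, with 4 events per candidate at 30 days, so the models are hypothesis-generating whatever the validation method. Nothing here bears on the primary endpoint or the sample size.

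**What to change.** In section 10.4.4, replace the testing-set sentence with a statement of internal validation on all patients:
- Fit each model to all patients with the outcome, and correct its accuracy for optimism by bootstrap. Repeated cross-validation is an acceptable alternative.
- Repeat the whole procedure in each resample: the AIC or BIC subset search for Models 2 and 3, and tree growing and pruning for Models 4 and 5.
- Report optimism-corrected AUC and calibration.
- Make the comparisons of Models 2 with 3 and 4 with 5, including net reclassification, on corrected values.

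If an external cohort was intended, name it instead. The cost is SAP wording and computing time. The bootstrap is already planned for other purposes, and no further patients or data are needed.

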## 10.2 STATISTICAL HYPOTHESES

- *Hypothesis 1: LUS guided patients will have less congestion, defined by LUS B-lines <15, than usual care patients at 6 hours after start of treatment. Other measures of congestion, such as serial LUS during hospitalization, physical exam, NTproBNP, and hemoglobin/hematocrit levels will be assessed to determine the superiority or additive value of LUS.*
- *Exploratory Hypothesis: Strategy-of-care patients will have more days alive and out of hospital (DAOOH) at 30 days.*
  - *Strategy-of-care patients will have more days alive and out of hospital (DAOOH) at 90 days.*
- *Hypothesis 2: Each site (n=4) will enroll ~2 patient per month for 18 months.*

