## 10.4 DESCRIPTION OF STATISTICAL METHODS

### 10.4.1 GENERAL APPROACH

Unless stated otherwise, two-sided p values < 0.05 will be considered statistically significant, without regard to multiple comparisons. Statistical tables and listings and analyses will be produced using SAS® release 9.1 or later (SAS Institute, Inc, Cary, NC, USA) or other validated statistical software.

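### The added value of B-lines is judged by net reclassification between data-selected models on an undefined testing set, so the result is either biased upward or has very little power

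*Combined protocol and SAP*

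**What the plan says.** Section 10.4.4 sets out five models for 30- or 90-day outcomes.

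- Model 1 holds all markers plus B-lines.
- Model 2 is the best-fitting main-effects model from a search over B-lines and the other markers. AIC and BIC are given only as examples of the criterion.
- Model 3 comes from a search over the other markers only, with no criterion stated.
- Models 4 and 5 are classification trees with and without B-lines.

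All five are to be evaluated on a testing set, which no section defines. The plan then says "Models 2 and 3, 4 and 5 will be compared (if there is a difference between models 2 and 3", with the same condition for the trees, in order "to understand the net reclassification rate". Inference is by bootstrap. The plan does not say whether each resample repeats the model search. Model 1 has no fixed counterpart without B-lines.

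Hypothesis 1 in Section 10.2 says that other measures of congestion "will be assessed to determine the superiority or additive value of LUS". Section 10.4.1 sets the general threshold: "two-sided p values < 0.05 will be considered statistically significant, without regard to multiple comparisons".

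**The concern.** Hypothesis 1 asks what B-lines add, but no pre-specified test isolates it. Model 2 differs from Model 3 in its B-line term only when the search has kept B-lines. A non-zero NRI is therefore reported only after the data, through signal or chance, have favoured them. On the fitting data, NRI carries no penalty for that selection. On a hold-out, a pilot of 130 patients leaves very few events to judge from. Section 3 says the pilot should supply what is needed to design a definitive trial. An inflated estimate, or a real contribution that is missed, would misinform that step.

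**Working it through.** **1. The plan's own figures (Section 10.5).** The plan states "With 59 patients in each of the two arms, we will have 81% power to detect an effect size of 2", meaning "25% in the usual care versus 50% in the strategy care". With mean proportion 0.375, z = [0.25 x sqrt(59) - 1.96 x sqrt(2 x 0.375 x 0.625)] / sqrt(0.25 x 0.75 + 0.50 x 0.50) = (1.920 - 1.342)/0.661 = 0.87. Power is 80.9%, so 81% reproduces. The plan adds "Considering a conservative 10% drop-out rate, we will need a total of 130 subjects": 118 x 1.1 = 129.8, or 130 (118/0.9 would give 132). With 10% lost, 130 x 0.9 = 117 are evaluable. The plan gives no power figure for the reclassification analysis.

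**2. Events available.** The plan states no event rate for these models. The Protocol Summary's background figure is nearly 25% dead or re-hospitalized at 30 days, used here as an assumption.

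- Events: 117 x 0.25 = 29, or 130 x 0.25 = 32.5.
- One-third hold-out: about 10 or 11 events.
- The tree paragraph speaks of B-lines and seven other markers, which it does not list. Eight terms give 29.25/8 = 3.7 to 32.5/8 = 4.1 events per term. Section 10.4.3 requires 10 for its own model.
- Ten events for each of eight terms would need 80 events, which is 80/117 = 68% of patients.

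**3. How often a worthless marker is kept.** AIC keeps a marker when twice its log-likelihood gain exceeds 2: P(chi-square on 1 df > 2) = 15.7%. BIC needs more than ln(117) = 4.76, a probability of about 3%.

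**4. Simulation.** Assumptions:

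- n = 117, about 28-31 events, and eight standardised markers with correlation 0 or 0.3.
- Two other markers have log-odds 0.5 and 0.4 per SD. B-lines have 0, 0.4 or 0.6.
- Models 2 and 3 are chosen by all-subsets AIC.
- NRI is category-free: mean sign of (Model 2 risk - Model 3 risk) in events, minus the same mean in non-events.
- NRI counts as positive if the lower bootstrap 95% limit exceeds 0, with the models held fixed.
- The comparator is the 1-df likelihood-ratio test (LRT) of the fixed eight- versus seven-marker model, two-sided 5%.
- 1,000 runs per row.

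| B-line log-odds | Correlation | AIC keeps B-lines | LRT | Same-data NRI, all trials | Same-data NRI, comparisons made | NRI on one-third hold-out, all trials |
|---|---|---|---|---|---|---|
| 0 | 0 | 16.8% | 5.2% | 4.4% | 26.2% | 0.5% |
| 0 | 0.3 | 17.1% | 6.1% | 4.3% | 25.1% | 0.9% |
| 0.4 | 0 | 60.6% | 39.6% | 29.0% | 47.9% | 7.1% |
| 0.4 | 0.3 | 55.1% | 30.4% | 21.0% | 38.1% | 6.3% |
| 0.6 | 0 | 87.9% | 75.2% | 57.3% | 65.2% | 18.5% |
| 0.6 | 0.3 | 83.2% | 63.1% | 43.4% | 52.2% | 15.4% |

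With worthless B-lines, the mean same-data NRI when they were selected was 0.31. On the hold-out, the false-positive rate among comparisons made was 3-5%.

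**5. Sensitivity.** With five other markers, 130 patients, an odds ratio of 1.61 per SD and a half-sample hold-out, power was 55% (LRT), 42% (same-data NRI) and 24% (hold-out NRI). With five other markers, 117 patients, log-odds 0.5 and a one-third hold-out, the figures were about 58%, 43% and 13%. The ordering did not change.

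**The case against.** **The testing set.** A reader might infer that the plan selects B-lines and then claims their value on the same data. The documents do not support that as a flat statement. The sentence just before the comparison sends all five models to a testing set, and a genuine hold-out essentially removes the selection bias. What stands is that the set is undefined, and that at this sample size a real one costs most of the power.

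**Conditional error rates.** A reader might also infer that NRI is wrong a quarter of the time or more when B-lines are useless. That figure comes from looking only at trials where B-lines were selected. The LRT conditioned in the same way fares no better: 0.05/0.157 = 32% after AIC selection. Over all trials the same-data NRI rate is about 4-5%. The error-rate argument is therefore modest. The biased estimate remains.

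**The condition on differing models.** If Models 2 and 3 coincide, NRI is exactly 0, so the clause is partly trivial. Section 10.4.4 also evaluates every model's accuracy, and plans ROC curves and a bootstrap comparison of markers, without that condition. This is fair; the remaining fault is that the null NRI would go unreported. The wording can also be read as forcing B-lines into Model 2. Same-data NRI was then positive in 7.6-7.7% of null trials against 2.5%, so the problem survives that reading.

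**A different question.** The LRT tests association given the other markers, not reclassification, and it cannot compare the trees. That stands, which is why a corrected change in AUC belongs beside it.

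**Conclusion.** The point holds in conditional form. As written, the NRI comparison could be run in two ways, and neither gives a reliable answer. On the fitting data, or with a bootstrap that does not repeat selection, the reported NRI is too high when B-lines add nothing. On a one-third hold-out it would usually miss a real contribution. The fixed-model LRT had more power in every scenario, with a false-positive rate of about 5-6%.

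The sizes rest on assumptions that the documents do not supply: effect sizes, correlations, the 25% event rate for these models, the split, and category-free NRI. More events, as would be expected at 90 days, would raise power. The LRT figures are for eight versus seven markers; a shorter list was not simulated. The analysis is exploratory, so the primary endpoint is unaffected and the priority is low.

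**What to change.** In Section 10.4.4:

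1. Name a short fixed marker list in keeping with the 10 events per covariate of Section 10.4.3. At about 29-33 events that allows two or three terms, B-lines included.
2. Always report the LRT of that model with versus without B-lines on all patients, with the B-line odds ratio per SD and its 95% CI.
3. Replace the undefined testing set by the change in AUC, with a bootstrap optimism correction that repeats any selection steps.
4. Label NRI and Models 2-5, trees included, as descriptive. Report the NRI also when it is zero.

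The cost is SAP wording and a simpler analysis, with no new data. The price is that NRI is no longer an inferential measure for comparison with papers that report it, and that the tree comparison has no formal test.

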#### 10.4.5 SAFETY ANALYSES

Hypotensive events will be reported per treatment arm as well as other safety events ascertained during the study. Continuous variables will be summarized by typical parameters such as mean, standard deviation and range and compared using two-sample T test (if the normality assumption holds) or Wilcoxon rank-sum test (if the normality assumption does not hold). Normality of distribution will be determined using the Kolmogorov-Smirnov goodness-of-fit test. Categorical data will be summarized by frequency and percentage and analyzed using the Chi-square or Fishers exact test, as appropriate.

As all cause mortality and re-hospitalizations will already be reported as part of the efficacy exploratory analyses, these will also be highlighted as safety analyses.

---

#### 10.4.6 ADHERENCE AND RETENTION ANALYSES

Missing data: We will compare relevant patient characteristics between those who stay in the study and those who drop out to examine whether there are characteristics that discriminate between the two groups. It is possible that the dropout mechanism does not depend on unobserved outcomes (Missing At Random, or MAR), where no bias will be introduced by ignoring the missing-data mechanism. We can simply use all observed outcomes for the analysis. Under circumstances where power loss is of concern, we will use a multiple imputation procedure to make use of all relevant observed variables to enhance power. The SAS procedure MI and MIANALYZE will be used for implementation of this procedure.

In case the dropouts are Missing Not At Random (MNAR), which means the likelihood of drop-out depends on an unobserved outcome, potential bias can be introduced if the miss-data mechanism is ignored. We will make various assumptions regarding the missing-data process. With these assumptions, we will fit proper models, either in the form of selection model, pattern mixture model, or latent variable model to account for the missing-data process. A sensitivity analysis will be conducted to compare the results based on different assumptions and models and assess the robustness of the inference.

---

